8.3 Reference Dates

The following reference dates are defined:

1. **Screening date** is defined as the eCRF provided date on which a subject was screened for trial entry. If screening procedures took several days, the first of these days is considered as screening date.
2. **Informed consent date** is defined as the date of Informed Consent signed by the subject collected on Informed Consent eCRF page.
3. **Treatment start date(time)** is defined as the date(time) of first dose of any study drug (Cy-Pep1 or pembrolizumab). **CyPep-1 treatment start date(time)** is defined as the date(time) of first dose of CyPep-1. **Pembrolizumab treatment start date(time)** is defined as the date(time) of first infusion of pembrolizumab.
4. **Treatment end date(time)** is defined as the date(time) of last dose of any study drug (Cy-Pep1 or pembrolizumab). **CyPep-1 treatment end date(time)** is defined as the date(time) of last dose of CyPep-1. **Pembrolizumab treatment end date(time)** is defined as the end date(time) of last infusion of pembrolizumab.
5. **End of study date** is defined as Date of study completion/discontinuation recorded on the End of Study Form in the eCRF.

Statistical Analysis Plan

SMS-0571/CyPep-1

V3.0 Final

04-Jun-2024

6. Age will not be calculated and will come directly from the eCRF. The eCRF uses the demographics assessment date at Screening as its reference date for age calculation.
7. Safety data, such as AEs and laboratory assessments, will use the treatment start date as a reference date.
8. Efficacy data will use the treatment start date as a reference date.
9. **Study day** will be based on treatment start date as a reference date.

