9.5 Medication Prior, Concomitant and Subsequent to Study Treatment

9.5.1 Medications Prior, Concomitant and Subsequent to Study Treatment

Medications prior, concomitant and subsequent to study treatment will be coded using the World Health Organization (WHO) Drug Dictionary (format and version specified in the *Data Management Plan*).

Medications prior to study treatment are those which have been identified to have been discontinued prior to the treatment start date(time). Medications concomitant to study treatment are those which have been identified to have been taken at any point during the period from treatment start date(time) until treatment end date(time) (both inclusive), including medications which started prior to the treatment start date(time) but are ongoing at first dose. Medications subsequent to study treatment are those which have been identified to have been started after the treatment end date(time). Partial dates will be imputed according to [APPENDIX 1. PARTIAL DATE CONVENTIONS](#) for the determination of medications prior, concomitant and subsequent to study treatment.

The incidence of use of medications prior, concomitant and subsequent to study treatment will be summarized by WHO Drug Dictionary Anatomic Therapeutic Chemical (ATC) Level 2 classification (i.e., therapeutic subgroup) and preferred name. A subject will be counted at most once at each level of reporting. Use of medications prior, concomitant and subsequent to study treatment will be summarized separately and presented by cohort/arm and overall for the SAF

All data of medications prior, concomitant and subsequent to study treatment will be provided together in a by-subject listing including the verbatim and preferred drug name and WHO ATC Class (ATC Level 2) for all subjects. Medications prior, concomitant and subsequent to study treatment will be flagged as such in the listing.

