Else impute *start datetime* as earliest possible datetime (i.e., 00:00 if time unknown, first day of month at 00.00 if time and day unknown or 1st of January at 00.00 if time, day and month are unknown).

For procedures, only impute start date (time is not collected for procedures).

Partial stop datetime

Impute *stop datetime* as latest possible datetime (i.e., 23:59 if time unknown, last day of month at 23.59 if day unknown or 31st December at 23.59 if day and month are unknown). If the imputed *stop datetime* falls after *end of study date*, the *stop datetime* is imputed with the *end of study date* at 23:59.

For procedures, only impute end date (time is not collected for procedures).

An algorithm for classifying medications and procedures is given in [Table 7](#) below.

Statistical Analysis Plan

SMS-0571/CyPep-1
V3.0 Final
04-Jun-2024

Table 7. Algorithm for Medications and Procedures Prior / Concomitant / Subsequent to Study Treatment

Stop date	Rule*
Known	If stop date(time) < treatment start date(time) , assign as prior. If treatment start date(time) <= stop date(time) <= treatment end date(time) , assign as concomitant. If treatment end date(time) < (imputed) start date(time) , assign as subsequent.
Partial	If imputed stop date(time) < treatment start date(time) , assign as prior. If treatment start date(time) <= imputed stop date(time) <= treatment end date(time) , assign as concomitant. If treatment end date(time) < (imputed) start date(time) , assign as subsequent.
Missing	If treatment end date(time) < (imputed) start date(time) , assign as subsequent. Else, assign as concomitant.

*For medications use datetime, for procedures use date.

Statistical Analysis Plan

SMS-0571/CyPep-1
V3.0 Final
04-Jun-2024

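### SAP Table 7 gives no category to medications or procedures that start by the last dose and stop after it, contrary to SAP 9.5.1 and 9.4.2

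*SAP*

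**What the plan says.** SAP 9.5.1 defines concomitant medications as those "taken at any point during the period from treatment start date(time) until treatment end date(time) (both inclusive", and adds that drugs begun earlier but ongoing at first dose are included. SAP 9.4.2 uses the same overlap idea for procedures. Both sections cite Appendix 1 for imputing partial dates. SAP 8.3 sets treatment end at the last dose of any study drug.

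Table 7 in SAP 13.1 (Appendix 1) is then presented as the algorithm for classifying medications and procedures. For a known stop date it has three rules:

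- Prior: "If stop date(time) < treatment start date(time) , assign as prior".
- Concomitant: "If treatment start date(time) <= stop date(time) <= treatment end date(time) , assign as concomitant".
- Subsequent: "If treatment end date(time) < (imputed) start date(time) , assign as subsequent".

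The Partial row repeats these with the imputed stop: "If treatment start date(time) <= imputed stop date(time) <= treatment end date(time) , assign as concomitant". Only the row for a missing stop date ends with a catch-all: "Else, assign as concomitant". Partial stops are imputed "as latest possible datetime (i.e., 23:59 if time unknown, last day of month at 23.59 if day unknown", and they are capped at the end of study date. Medications are compared by datetime and procedures by date.

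**The concern.** The concomitant rule in the Known and Partial rows looks only at the stop date and requires it to fall inside the treatment period. The subsequent rule looks only at the start date and requires it to fall after treatment end. A record that straddles treatment end satisfies neither, and it is not prior.

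The data to be collected make this pattern possible. Treatment end is the last dose, not the End of Treatment visit. Protocol 5.6 has concomitant medications recorded until the follow-up visit, which the schedule of assessments places at least 30 days after the last dose (or until End of Treatment, if that falls more than 30 days after it). Stop dates after the last dose will therefore be in the database. For subjects still on treatment at a data cut, SAP 8.7 can set treatment end at the last recorded dose, so a drug spanning that dose and stopped before the cut-off is in the same position.

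At stake are the descriptive counts of concomitant medications and procedures. Protocol 8.1.7 promises these by type for the safety set, and Protocol 5.6 names some of the drugs, such as AE treatments and anti-infectives, as being of special interest.

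**Working it through.** The plan states no figure on this point, so the check is one of logic. Write TS for treatment start, TE for treatment end.

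**Rules side by side, for a record with a start and a stop**

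| Category | Table 7, Known and Partial rows | SAP 9.5.1 and 9.4.2 text |
|---|---|---|
| Prior | stop < TS | stop < TS |
| Concomitant | TS ≤ stop ≤ TE | start ≤ TE and stop ≥ TS |
| Subsequent | start > TE | start > TE |

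The two columns differ only where start ≤ TE < stop.

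**One record.** Assume treatment from Day 1 to Day 29 and a drug taken from Day 20 to Day 40.

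- Prior: 40 < 1 is false.
- Concomitant: 1 ≤ 40 ≤ 29 is false.
- Subsequent: 20 > 29 is false.
- Table 7 result: no category.
- Text result: 20 ≤ 29 and 40 ≥ 1, so concomitant.
- The same drug with a missing stop date: 20 > 29 is false, so the catch-all makes it concomitant. The less complete record is classified correctly and the complete one is not.

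**All records on an illustrative grid.** Same treatment period, starts from Day -30, stops up to Day 60, every integer pair with start ≤ stop.

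| Pairs | Count | Table 7 | Text |
|---|---|---|---|
| Stop before Day 1 | 31 × 32 / 2 = 496 | prior | prior |
| Stop on Day 1 to 29 | 1,334 | concomitant | concomitant |
| Start by Day 29, stop on Day 30 to 60 | 60 × 31 = 1,860 | none | concomitant |
| Start after Day 29 | 31 × 32 / 2 = 496 | subsequent | subsequent |

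The 1,860 split into 31 × 31 = 961 starting before first dose and 29 × 31 = 899 starting during treatment. With a missing stop date, the 60 starts by Day 29 are concomitant and the 31 later starts subsequent under both columns. The counts show where the gap lies. They depend on the grid chosen and say nothing about how often the pattern will occur in the trial.

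**Unknown stop time on the last-dose day.** Assume the last dose at 10:00 on Day 29 and a drug started at 09:00 that day, stopped the same day at an unknown time. The stop is imputed to 23:59, which is later than 10:00. Prior, concomitant and subsequent are all false, so the record has no category. This applies to medications only, because no time is collected for procedures. Imputation of an unknown day to the end of the month can push a stop past treatment end in the same way.

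**After correction.** With concomitant written as start ≤ TE and stop ≥ TS, the grid gives 496 prior, 1,334 + 1,860 = 3,194 concomitant and 496 subsequent. The total is 4,186, with 0 pairs outside exactly one category.

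**The case against.** The strongest reply is that the body of the SAP already holds the right rule. Sections 9.5.1 and 9.4.2 define concomitant by overlap, they cite Appendix 1 for imputing partial dates, and nothing says that Table 7 overrides them. A programmer working from the text would classify these records correctly, and an unflagged line in the medication listing could reveal the error. This stands as a limit on the consequence: loss from the tables is conditional on literal programming. It does not remove the conflict, because the SAP itself introduces Table 7 as the classifying algorithm and no section reconciles the two.

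Several stronger readings are tempting but not supported:

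- **That the pattern is common.** The documents give no count. Drugs still ongoing with no stop date are safe through the Missing row.
- **That drugs given for the AE that ended treatment are lost.** Dosing is intermittent, so such a drug may well start after the last dose, and it is then subsequent under both the text and Table 7. Only a course begun on or before the last dose and finished later, such as a tapered corticosteroid, falls in the gap.
- **That anticancer therapies vanish from summary tables.** SAP 9.4.3 and 9.5.2 only list concomitant and subsequent anticancer procedures and therapies, and prior ones come from dedicated eCRF pages.
- **That PFS or duration of response is affected.** The censoring rules in SAP Appendix 2 refer to new protocol-excluded anticancer treatment and its start, not to a Table 7 category.

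**Conclusion.** The point holds as an internal contradiction in the SAP. In the Known and Partial rows, every medication or procedure with start ≤ treatment end < stop is left without a category, while the SAP's own definitions make it concomitant. Because the Missing row has a catch-all, this looks like an omission, not a choice.

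If Table 7 is coded as written, the concomitant medication and procedure counts would be too low by the number of subjects whose only qualifying record at a given reporting level is of this kind. Those records would appear in no prior, concomitant or subsequent summary, and in the medication listing they would carry no flag. The size cannot be estimated from the documents. The effect is confined to descriptive tables and flags: no endpoint, sample size or error rate changes. The conclusion assumes only that Table 7 is read literally and that no programming specification outside these documents already corrects it.

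**What to change.** In the Known and Partial rows of Table 7, replace the concomitant rule with: assign as concomitant if (imputed) start ≤ treatment end and (imputed) stop ≥ treatment start. Equivalently, keep the prior and subsequent rules and add the Missing row's catch-all as the last line of both rows. Either version restores agreement with SAP 9.5.1 and 9.4.2, and both resolve the 23:59 case.

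The cost is one line in each of two table rows and the matching program code, made before the final analysis. No new data are needed. If the mid-study outputs were programmed from Table 7, a query for records with start ≤ treatment end < stop would show whether any were dropped.

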13.2 APPENDIX 2. CENSORING RULES: DOR and PFS

Censoring rules for DOR and PFS are presented in [Table 8](#) below.

Table 8. Censoring Rules for DOR and PFS

#	Situation	Date of Event (PD/Death) or Censoring	Outcome: Event (PD/Death) or Censored
1	No (or inadequate) baseline tumor assessments and the subject has not died	Treatment Start Date	Censored
2	No post-baseline assessments and the subject has not died	Treatment Start Date	Censored
3	iUPD followed by discontinuation due to clinical disease progression, radiological disease progression or death within 8 weeks	Date of assessment of progression ¹	Event
4	iUPD without subsequent iSD, iPR or iCPD and followed by:	Date of assessment of progression ¹	Event
	1. Treatment discontinuation due to clinical instability (i.e., clinical disease progression, radiological disease progression). 2. No further response assessments (due to subject refusal, protocol non-compliance, or subject death). 3. Next timepoint responses all equal to iUPD. 4. Subject death from cancer.		
5	No iUPD as described in #3 and #4, no iCPD or death and no new protocol excluded anticancer treatment documented	Date of last 'adequate' assessment of response ²	Censored
6	No iUPD as described in #3 and #4, no iCPD or death and new protocol excluded anticancer treatment documented	Date of last 'adequate' assessment of response ² on or prior to starting anticancer therapy	Censored
7	New protocol excluded anticancer treatment started (prior to iUPD as described in #3 and #4, iCPD or death) ³	Date of last 'adequate' assessment of response ² on or prior to starting anticancer therapy	Censored
8	iCPD documented between scheduled visits	Date of assessment of progression ¹	Event
9	Death before first iCPD assessment	Date of death	Event
10	Death between adequate assessment visits	Date of death	Event
11	Death or progression after two missed visits (with 1-week window) where last assessment is not iUPD	Date of last 'adequate' assessment of response ² prior to missed assessments	Censored

¹The earliest of

- (i) Date of radiological assessment showing new lesion (if progression is based on new lesion); or
- (ii) Date of radiological assessment showing unequivocal progression in non-target lesions, or
- (iii) Date of last radiological assessment of measured lesions (if progression is based on increase in sum of measured lesions).

²An adequate assessment is defined as a radiological assessment where iCR, iPR, or iSD was determined.

³If iCPD and subsequent protocol excluded anti-cancer therapy occur on the same date, assume the progression was documented first.

Statistical Analysis Plan

SMS-0571/CyPep-1
V3.0 Final
04-Jun-2024

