On the confirmatory scans, the participant will be classified as progression confirmed (with an overall response of iCPD), or as showing persistent unconfirmed progression (with an overall response of iUPD), or as showing disease stability or response (iSD/iPR/iCR).

Confirmation of Progression

Progression is considered confirmed, and the overall response will be iCPD, if ANY of the following occurs:

- Any of the factors that were the basis for the initial iUPD show worsening
 - For target lesions, worsening is a further increase in the sum of diameters of ≥ 5 mm, compared to any prior iUPD time point
 - For non-target lesions, worsening is any significant growth in lesions overall, compared to a prior iUPD time point; this does not have to meet the “unequivocal” standard of RECIST 1.1
 - For new lesions, worsening is any of these:
 - An increase in the new lesion sum of diameters by ≥ 5 mm from a prior iUPD time point
 - Visible growth of new non-target lesions
 - The appearance of additional new lesions
- Any new factor appears that would have triggered PD by RECIST 1.1

Persistent iUPD

Progression is considered not confirmed, and the overall response remains iUPD, if:

- None of the progression-confirming factors identified above occurs AND
- The target lesion sum of diameters (initial target lesions) remains above the initial PD threshold (by RECIST 1.1)

Additional scans for confirmation are to be scheduled 4 to 8 weeks from the scans on which iUPD is seen. This may correspond to the next visit in the original visit schedule. The assessment of the subsequent confirmation scan proceeds in an identical manner, with possible outcomes of iCPD, iUPD, and iSD/iPR/iCR.

Resolution of iUPD

Progression is considered not confirmed, and the overall response becomes iSD/iPR/iCR, if:

- None of the progression-confirming factors identified above occurs, AND
- The target lesion sum of diameters (initial target lesions) is not above the initial PD threshold.

The response is classified as iSD or iPR (depending on the sum of diameters of the target lesions), or iCR if all lesions resolve.

In this case, the initial iUPD is considered to be pseudoprogression, and the level of suspicion for progression is “reset”. This means that the next visit that shows radiographic progression, whenever it occurs, is again classified as iUPD by iRECIST, and the confirmation process is repeated before a response of iCPD can be assigned.

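### Row 4 of SAP Tables 8 and 9 leaves iCR out of the responses that cancel an iUPD, so a later event can be back-dated to a progression that had already resolved

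*SAP*

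**What the plan says.** SAP Appendix 2 (Table 8) sets the event and censoring rules for PFS and duration of response. Appendix 3 (Table 9) does so for duration of stable disease. Row 4 opens identically in both: "iUPD without subsequent iSD, iPR or iCPD and followed by". In Table 8 it is completed by any one of four sub-conditions:

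1. The subject stops treatment because the disease has progressed, clinically or on imaging; no time limit is set.
2. Scanning ends after the iUPD, worded as "No further response assessments (due to subject refusal, protocol non-compliance, or subject death".
3. Every scan after the iUPD is again read as iUPD.
4. The last is worded as "Subject death from cancer", and it too carries no time limit.

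The outcome is an event, dated at "Date of assessment of progression", which is the iUPD itself. Table 9 keeps sub-conditions 1 to 3, drops death from the second, and has no fourth.

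Protocol Appendix D, on resolution of iUPD, says that when no confirming factor occurs and the target sum is not above the threshold, "the overall response becomes iSD/iPR/iCR". The first iUPD is then pseudoprogression and the suspicion of progression is reset. The protocol's efficacy text (synopsis and section 6.2) likewise disregards a first PD when the lesions are unchanged or smaller at reassessment.

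**The concern.** Three responses resolve an iUPD under the protocol, but only two of them, iSD and iPR, are named in row 4. The best of the three is missing, and nothing suggests that this was intended.

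The row also conflicts with the rest of the SAP. Sections 10.1.2, 10.1.4 and 10.2.2 describe the progression event as an iUPD that is later confirmed. Footnote 2 of both tables accepts iCR as an adequate assessment. Section 4.3 states that the SAP and protocol do not differ.

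At stake is the date, and in one route the existence, of a progression event in a subject whose early progression had cleared. Such a subject could have a best overall response of iCR and a progression event dated before that response. The wording also carries into the censoring rows that refer back to row 4 (rows 5 to 7 of Table 8, rows 6 to 8 of Table 9).

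**Working it through.** The plan gives no figure to reproduce, so the check applies row 4 literally to response sequences, first as written and then with iCR added.

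**Inputs.** Row 4 of each table as above; scans every 8 weeks with a confirmatory scan 4 weeks after PD (protocol); time in months = (end date - start date + 1) / 30.4375 (SAP sections 8.4, 10.1.2, 10.2.2). The sequences are assumptions, not trial data. All start with iUPD at week 8. Row 3 does not decide C, D or E, because the later discontinuation or death falls outside its 8-week window.

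| | After iUPD at week 8 | Table 8, row 4 | Table 9, row 4 | Week-8 match once iCR is added |
|---|---|---|---|---|
| A | iCR weeks 12-32, ongoing | not met | not met | none |
| B | iCR weeks 12-24, then refuses scans | not met | not met | none |
| C | iCR weeks 12-48, then cancer death | met (sub-condition 4), week 8 | not met | removed |
| D | iCR weeks 12-48, then discontinues for clinical progression, no new iUPD | met (1), week 8 | met (1), week 8 | removed |
| E | iCR weeks 12-40, new iUPD week 48, discontinues for PD | met (1), weeks 8 and 48 | met (1), weeks 8 and 48 | removed; week 48 stays |
| F | iCR weeks 12-24, iUPD week 48, iCPD week 52 | not met | not met | none |
| G | iPR weeks 12-16, iUPD week 48, discontinues for PD | met (1), week 48 only | met (1), week 48 only | none |

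E and G isolate the gap. With iPR as the resolving response, the week-8 iUPD drops out. With iCR it stays in.

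**Why A and B escape.** An iCR scan after the iUPD is itself a further response assessment, so sub-condition 2 fails. It is not an iUPD, so sub-condition 3 fails. The subject is censored at the last iCR (row 5 of Table 8, row 6 of Table 9). After an iCR, only sub-conditions 1 and 4 can still be met.

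**Size in sequence E.**
- PFS from the week-8 iUPD: (56 + 1) / 30.4375 = 1.87 months.
- PFS from the week-48 iUPD: (336 + 1) / 30.4375 = 11.07 months.
- Duration of response from the week-12 iCR to week 8: (56 - 84 + 1) / 30.4375 = -0.89 months.
- Duration of response from the week-12 iCR to week 48: (336 - 84 + 1) / 30.4375 = 8.31 months.

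The SAP sets no order between matching rows or between two matching iUPDs. Section 8.4 follows time-to-event endpoints to the first event or censoring, so a programmer could well take week 8.

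**Date or count.** In E there is an event either way and only its date moves. In C the death is already an event under rows 9 and 10, so row 4 back-dates it. The exception is a death after two missed visits, which row 11 would censor; rows 4 and 11 then conflict. In D the count changes: as written the subject has an event at 1.87 months, and with iCR added is censored at the week-48 iCR, 11.07 months.

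**The case against.** The strongest reply is that this is a drafting slip with little reach. The SAP's own endpoint definitions and protocol Appendix D point to the right answer, a negative duration of response would be noticed in programming, and the endpoints are secondary (duration of response, duration of stable disease) or exploratory (PFS), summarised by Kaplan-Meier methods without hypothesis tests. That is fair and sets the weight of the point. It does not repair the row: no SAP text adds iCR to it. Nor would every error be visible. A response, then iUPD, then iCR, then discontinuation for progression would give a positive but shortened duration.

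A reader might infer more than the documents support:

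- **That any complete response after pseudoprogression becomes a progression event.** It does not. A subject in continuing iCR, or with iCR and then no further scans, is censored at the last iCR.
- **That a later cancer death adds an event to all three endpoints.** In Table 8 it mostly re-dates a death already counted. Table 9 has no cancer-death sub-condition and its row 9 censors deaths, so duration of stable disease is reached only through sub-condition 1.
- **That the event proportion moves by 6 to 11 points.** Those figures are one subject's share of Arm A (1/18 = 5.6%, 1/9 = 11.1%). They apply only to the route in D, and not to duration of response, which is computed in confirmed responders only. No shift in a median has been shown.

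**Conclusion.** The omission is real, stands in both tables, and contradicts protocol Appendix D and the SAP's own definitions. Its consequence is narrow. The iUPD must be followed by iCR with no later iSD, iPR or iCPD, and the subject must then discontinue for progression (all three endpoints) or die of cancer (PFS and duration of response). The usual result is a later event dated too early, by about 9 months of PFS in the assumed sequence (11.07 - 1.87 = 9.20). Row 11 deaths aside, the event count changes only when such a subject discontinues for progression with no new iUPD, iCPD or death.

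The documents give no frequency for this path. That it is rare is a judgement, based on small, heavily pre-treated arms and the number of conditions that must coincide. The week numbers are illustrative; the matching of rows follows from the wording alone. This is a minor wording error, worth correcting before database lock.

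**What to change.** In row 4 of Table 8 and row 4 of Table 9, insert iCR so that the later responses taking an iUPD out of the rule are iSD, iPR, iCR or iCPD. Rows that refer back to row 4 then follow without further edits. The cost is one word in two tables and the matching line of derivation code. It needs no new data and changes nothing for subjects who have no iCR after an iUPD.
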